Bayley Scales of Infant Development (BSID), 4th Edition. 30-70 minutes to administer. The BSID-IV is an internationally recognized, norm referenced set of tests designed to assess developmental domains from one month to 42 months of age. The BSID-IV includes assessment of cognitive, motor (fine motor and gross motor), social-emotional, adaptive, and language (receptive and expressive communication) subscales. All domains and subscales will be assessed. The administration of the developmental items on the Bayley will be conducted together with a researcher trained in the administration of the measure, the caregiver, and the child. Administration will be video-taped and scored at a later time in order to minimize length of in-person contact. The BSID-IV is a newly released version of the BSID-III, of which the score sheet and description are included in this application as attachments. We do not yet have access to the BSID-IV equivalents of these materials as the release of our funding to purchase the BSID IV is contingent on IRB approval. However, the differences between the III and the IV are noted in this publisher webinar (available at: https://youtu.be/Rp3QRz7qHhg) and are listed in the attached publisher presentation. These differences include shorter administration time, fewer items in several of the domains, a digital option for administration and scoring, and a more sensitive scoring scheme to identify disability. Similar to the III, the IV continues to allow for administration of structured test items in the five developmental domains described above using a standard kit, direct observation of behaviors and milestones, and active participation of the caregiver in the evaluation process. The BSID-IV has strong psychometric properties and has been empirically validated for our study population. Once the BSID-IV has been purchased, our research team will submit the scoring and overview materials upon a subsequent IRB modification.

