	This agreement should be available upon request from the IRB. Examples: a Data Use Agreement, Repository Gatekeeping form, or documented email.
	There are written policies and procedures for the repository/database/data management center that prohibit the release of the identifiers (or identifying link). This includes situations involving an Honest Broker.
	There are other legal requirements prohibiting the release of the identifiers or key. Describe them below.
b. Will you or an	y study team members obtain any direct or indirect identifiers?
X Yes	ightarrow If yes, describe which identifiers and for which data/specimens.
_	Members of the research team will obtain direct identifiers via name and contact information, in order to recruit subjects. Indirect identifiers will then be assigned from a master list of subjects. The research team will obtain indirect identifiers via a subject code after consent is documented. The research team will obtain audio recordings of interviews and video recordings of the Bayley developmental assessments which may include direct identifiers. We will also obtain study data in the form of surveys, developmental assessments, and observational assessment which will use indirect identification.
No	→ If no, select the reason(s) why you (and all members of your team) will not obtain direct or indirect identifiers.
	There will be no identifiers.
	Identifiers or the key have been (or will have been) destroyed before access.
	There will be an agreement with the holder of the identifiers (or key) that prohibits the release of the identifiers (or key) under any circumstances.
	This agreement should be available upon request from the IRB. Examples: a Data Use Agreement, Repository Gatekeeping form, or documented email.
	There are written policies and procedures for the repository/database/data management center that prohibit the release of the identifiers (or identifying link). This includes situations involving an Honest Broker.
	There are other legal requirements prohibiting the release of the identifiers or key. Describe them below.

c. If any identifiers will be obtained, indicate how the identifiers will be stored (and for which data). NOTE: Do not describe the data security plan here – that information is requested in section 9.6.

Identifiers will be stored with the data. Describe the data to which this applies:

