Because we are collecting audio and video data, this may be inherently identifiable. This data will be stored directly on a secured and encrypted university server.

Identifiers and study data will be stored separately but a link will be maintained between the identifiers and the study data (for example, through the use of a code). Describe the data to which this applies:

For all remaining data, each subject will be assigned an indirect identifier in the form of a participant code and pseudonym. A master list of the subject's direct and indirect identifiers will be kept separately from the data, in a locked file cabinet inside a locked office, or electronically on a secure and encrypted university server. This applies to all data collected in the study.

Identifiers and study data will be stored separately, with no link between the identifiers and the study data. Describe the data to which this applies:

d. Research collaboration. Will individuals who provide coded information or specimens for the research also collaborate on other activities for this research? If yes, identify the activities and provide the name of the collaborator's institution/organization.

Examples include but are not limited to: (1) study, interpretation, or analysis of the data that results from the coded information or specimens; and (2) authorship on presentations or manuscripts related to this work.

N/A

5.7 Protected Health Information (PHI). Will participants' identifiable PHI be accessed, obtained, used, or disclosed for any reason (for example, to identify or screen potential subjects, to obtain study data or specimens, for study follow-up) that does not involve the creation or obtaining of a Limited Data Set?

PHI is individually identifiable healthcare record information or clinical specimens from an organization considered a "covered entity" by federal HIPAA regulations, in any form or media, whether electronic, paper, or oral. You must answer yes to this question if the research involves identifiable health care records (e.g., medical, dental, pharmacy, nursing, billing, etc.), identifiable healthcare information from a clinical department repository, or observations or recordings of clinical interactions.

 \rightarrow If no, skip the rest of this question; go to question 5.8

 \rightarrow If yes, answer all of the questions below.

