If yes, the UW IRB expects subjects to be informed of this possibility in the consent form or during the consent process, unless you provide a rationale for not doing so:

Members of the research team are licensed rehabilitation professionals and considered mandated reporters of suspected or witnessed abuse. Although it is not anticipated that the research team is likely to learn of these events while conducting the research, if they are suspected or witnessed, we are obligated to report. Language describing this process is included in the consent/permission document.

9.4 Retention of identifiers and data. Check the box below to indicate assurance that any identifiers (or links between identifiers and data/specimens) and data that are part of the research records will not be destroyed until after the end of the applicable records retention requirements (e.g. Washington State; funding agency or sponsor; Food and Drug Administration). If it is important to say something about destruction of identifiers (or links to identifiers) in the consent form, state something like "the link between your identifier and the research data will be destroyed after the records retention period required by state and/or federal law."

This question can be left blank for conversion applications (existing paper applications that are being "converted" into a Zipline application.)

See the "Research Data" sections of the following website for UW Records management for the Washington State research rectords retention schedules that apply in general to the UW (not involving UW Medicine data): http://f2.washington.edu/fm/recmgt/gs/research?title=R

See the "Research Records and Data" information in Section 8 of this document for the retention schedules for UW Medicine Records: https://www.uwmedicine.org/recordsmanagementuwm-records-retention-schedule.pdf

X Confirm

9.5 Certificates of Confidentiality. Will a federal Certificate of Confidentiality be obtained for the research data? NOTE: Answer "No" if the study is funded by NIH or the CDC, because all NIH-funded and CDC-funded studies automatically have a Certificate.

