	If any of the boxes are checked: Provide the name and institutional affiliation of a physician anesthesiologist who is a member of the research team or who will serve as a safety consultant about the interactions between the research procedures and the general or regional anesthesia of the subject- patients. If the procedures will be performed at a UW Medicine facility or affiliate, the anesthesiologist must be a UW faculty member, and the Vice Chair of Clinical Research in the UW Department of Anesthesiology and Pain Medicine must be consulted in advance for feasibility, safety and billing.
	** If the box about radio-isotopes is checked: the study team is responsible for informing in advance all appropriate clinical personnel (e.g., nurses, technicians, anesthesiologists, surgeons) about the

administration and use of the radio-isotope, to ensure that any personal safety issues (e.g.,

pregnancy) can be appropriately addressed. This is a condition of IRB approval.

10.6 Data and Safety Monitoring. A Data and Safety Monitoring Plan (DSMP) is required for clinical trials (as defined by NIH). If required for this research, or if there is a DSMP for the research regardless of whether it is required, upload the DSMP to *Zipline*. If it is embedded in another document being uploading (for example, a Study Protocol) use the text box below to name the document that has the DSMP. Alternatively, provide a description of the DSMP in the text box below.

This study is a clinical trial funded by the NIH. The required DSMP will be uploaded to zipline.

10.7 Un-blinding. If this is a double-blinded or single-blinded study in which the participant and/or relevant study team members do not know the group to which the participant is assigned: describe the circumstances under which un-blinding would be necessary, and to whom the un-blinded information would be provided.

N/A

- **10.8 Withdrawal of participants.** If applicable, describe the anticipated circumstances under which participants will be withdrawn from the research without their consent. Also, describe any procedures for orderly withdrawal of a participant, regardless of the reason, including whether it will involve partial withdrawal from procedures and any intervention but continued data collection or long-term follow-up.

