ID: STUDY00011386 Early Powered Mobility for Toddlers With Cerebral Palsy Using the Permobil® Explorer Mini and a Modified Ride-On Car

Statistical Analysis Plan Document Date: 12/1/2020

Statistical Design and Power

Data Analysis:

All statistical analyses will be conducted using SPSS (version 26.0 IBM, Armonk, NY). Descriptive participant characteristics (e.g., age, sex, race/ethnicity, CP subtype, GMFCS-level) will be summarized as categorical variables.

Aim 1: Developmental, activity and participation outcomes

Sample size justification: Since the current proposal is a pilot study, there are no previous data to conduct a power analysis on the potential change of developmental, activity and participation outcomes as a result of using different powered mobility devices.

Analysis for measures assessed in Aim 1 will include descriptive statistics. Data will be assessed for normality and symmetry. If normality assumptions are met, we will use parametric statistics to examine between- and within-subject effects. If assumptions are not met, we will use the non-parametric equivalent of the planned analyses. We will calculate three separate analyses to examine changes in_developmental, activity and participation outcomes. (1) Separate 2 (group: 1, 2) x 3 (time: T0, T1, T2) repeated measures MANOVAs will be calculated to determine between- and within-subject changes on mean scores of developmental, activity and participation outcomes. (2)_Stratification into low and high usage groups will occur based on mean device use data. We will use these stratified groups to run our analyses to determine if device use is related to developmental, activity and participation outcomes. Separate 2 (group: low usage, high usage) x 3 (time: T0, T1, T2) repeated measures MANOVAs will be calculated to determine between- and scores of developmental, activity and participation outcomes. Separate 2 (group: low usage, high usage) x 3 (time: T0, T1, T2) repeated measures MANOVAs will be calculated to determine between- and within-subject changes on mean scores of developmental, activity and participation outcomes. Post-hoc analyses (i.e. Bonferonni correction) will be used for the above analyses to control for the type I error rate and determine where the significant differences exist. (3) We will also use visual analysis to determine if clinically significant differences exist.

Aim 2: Use patterns (frequency, duration, environment) & families' perspective and experiences

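### Bayley sessions are already video-taped and scored later; scoring coded recordings in random order would be a cheap, optional way to reduce scorer lean in the Aim 1 time effect

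*Protocol*

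**What the plan says.** Protocol 5.1 (Dependent Measures, BSID-IV) has the assessment "conducted together with a researcher trained in the administration of the measure, the caregiver, and the child". On scoring it says: "Administration will be video-taped and scored at a later time in order to minimize length of in-person contact". The scorer is not named, and neither the scoring order nor the scorer's knowledge of visit and device order is mentioned. The scoring documents are still to come: "our research team will submit the scoring and overview materials upon a subsequent IRB modification".

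Three other parts of the protocol bear on who scores and what is kept:

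- **10.7 (un-blinding)** asks blinded studies to "describe the circumstances under which un-blinding would be necessary, and to whom the un-blinded information would be provided". The answer is N/A.
- **12.3 (UW study team)** lets research assistants and co-investigators carry out every study procedure. It does not assign scoring.
- **5.6 and 9.4** cover the recordings. In 5.6.b, "The research team will obtain audio recordings of interviews and video recordings of the Bayley developmental assessments which may include direct identifiers"; in 5.6.c, "This data will be stored directly on a secured and encrypted university server"; and in 9.4 the team confirms that "data that are part of the research records will not be destroyed until after the end of the applicable records retention requirements".

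The SAP (Aim 1) crosses device order (2 groups) with visit (T0, T1, T2): "repeated measures MANOVAs will be calculated to determine between- and within-subject changes on mean scores of developmental, activity and participation outcomes". It says nothing about masked or random-order scoring. It adds Bonferroni-corrected post-hoc comparisons and states that no earlier data exist for an Aim 1 power analysis.

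**The concern.** Separating scoring from administration is usually the hard part of masked assessment, and this plan already does it for another reason. What is missing is the easy part: hiding which visit a recording comes from and which device came first.

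Aim 1 looks at change within each child across three visits. Both sequences receive both devices, so no untreated group shares a scorer's expectation that later visits should look better. Such an expectation would be read as developmental change. The Bayley is the Aim 1 measure where masking is practical, because the other two (CEDL and YC-PEM) are caregiver surveys.

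**Working it through.** **Inputs from the documents.** There are 18 children (Protocol 2.7), randomised 3 and 3 at each site (Protocol 5.1). Three sites give 9 per sequence. There are three visits, and Bayley administration takes 30 to 70 minutes (Protocol 5.1). The post-hoc correction is Bonferroni (SAP, Aim 1).

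**Inputs the documents do not give.** There is no SD of Bayley change, no scorer reliability, no scorer lean and no Aim 1 effect size. The plan therefore has no figure of its own to reproduce, and everything below is in units of the SD of within-child T0-T2 change.

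**Step 1: where a lean goes.** Let a scorer credit T2 by L more than T0, equally for all children. Write D1 and D2 for the true mean changes in the two sequences.

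- Time effect: ((D1 + L) + (D2 + L))/2 = (D1 + D2)/2 + L, so the bias is L.
- Order contrast: (D1 + L) − (D2 + L) = D1 − D2, so the bias is 0.

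This holds whatever the true change is. A simulation (40,000 runs per setting, 2 × 9 children, true change 0 and 1 SD, leans 0 to 0.3 SD) agreed. Bias in the time effect matched the lean to within 0.002 SD. Bias in the order contrast was within 0.004 SD of zero, and its rejection rate was 4.8-5.1%. This confirms the algebra; it is not evidence that a lean exists.

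**Step 2: a scale for L.** The mean change is pooled over two sequences of 9, with 18 − 2 = 16 df.

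- Unadjusted 95% half-width: t(0.975, 16)/√18 = 2.120/4.243 = 0.500 SD.
- Bonferroni, assuming three pairwise visit contrasts and the same 16 df: t(1 − 0.05/6, 16)/√18 = 2.673/4.243 = 0.630 SD.

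| Assumed lean (SD) | Share of 0.500 | Share of 0.630 |
|---|---|---|
| 0.05 | 10% | 8% |
| 0.1 | 20% | 16% |
| 0.2 | 40% | 32% |
| 0.3 | 60% | 48% |

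Correcting across subscales as well would lower the shares further.

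**Step 3: workload.** 18 × 3 = 54 recordings. At 30 minutes each, 54 × 0.5 h = 27 h. At 70 minutes, 54 × 70/60 h = 63 h. The present plan already has to score this material. If someone other than the scorer had to review every recording in full to remove cues, that would be a second pass of up to 27-63 h.

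**The case against.** The case against has six parts.

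1. **No lean is shown.** This is true. The table rests on assumed values, and a lean of 0.1 SD or less would hardly matter.
2. **Masking would be partial.** This stands. The administrator and caregiver know the visit, speech may reveal a device, and toddlers visibly grow over two 8-week phases. How much lean would survive cannot be estimated.
3. **The inferential gain is small.** This largely stands. The measure protected is an uncontrolled before-after change in a pilot, and only the Bayley items scored from video benefit.
4. **The work may be understated.** This stands if every recording must be trimmed. It can mostly be avoided by filming only the Bayley session with no device in view.
5. **The record is incomplete.** This also stands. The protocol is a lay-language IRB form, and the BSID-IV scoring materials were deferred.
6. **Nothing is lost by waiting.** This is partly right. The recordings are kept, so masked re-scoring stays possible, but it would mean doing the work twice.

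A reader might infer from the N/A at 10.7, together with the broad roles in 12.3, that whoever ran a child's visits will score them knowingly. The documents do not support that. Item 10.7 concerns knowledge of assigned group, not of visit, and 12.3 describes general roles for UW staff without assigning scoring. The supportable statement is that the present text is silent.

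**Conclusion.** The point holds as an optional improvement. Delayed video scoring is planned, masking of the scorer is not described, and any lean toward later visits would enter the Aim 1 time effect one for one. Its size is unknown. If it were 0.1 to 0.3 SD of within-child change, it would take up 20% to 60% of the unadjusted half-width, or 16% to 48% under Bonferroni. These shares assume all 18 children complete, the lean is the same for all of them, and (for the second range) three pairwise visit contrasts.

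Three stronger readings should be resisted:

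- **Aim 1 is invalid, or its Bayley results are known to be biased.** The documents contain no evidence of a lean.
- **The randomised comparison is compromised.** A lean common to both sequences cancels from the order contrast. Only a lean that differed by sequence would affect it.
- **Masked scoring would let the T0-T2 change be credited to the devices.** It would not, because there is still no untreated group.

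**What to change.** In Protocol 5.1, after the sentence on video, add:

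*Bayley recordings are given random file codes without date or visit label and are raw-scored in random order after the child's T2 visit, by an existing trained team member who is not told visit or device order and, where the existing team allows, did not run that child's visits; raw scores are recorded before age-norming.*

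Record only the Bayley session, with no device in view, and trim obvious device or visit cues only where that is simple. Age-norming comes after raw scoring because age reveals the visit. Caregiver-reported Bayley items, CEDL, YC-PEM and in-visit ALP staging stay as planned. The text can go into the IRB modification already foreseen for the scoring materials. Any recordings already scored unmasked can be re-scored this way.

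**Cost.** The sample size, the visits and the SAP tests do not change, and no new staff are required. The added work is coding 54 files and setting the scoring order, plus any trimming by someone other than the scorer (27-63 h at most). Scores become available only after T2. The number of Bayley-trained staff per site is not given; if the only available scorer ran the visits, most of the benefit is lost. Sending identifiable child videos between sites instead would have to be described to the IRB.

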7 ASSENT OF CHILDREN (MINORS)

Go to Section 8 if your research does not involve children (minors).

- **7.1 Assent of children (minors)**. Though children do not have the legal capacity to "consent" to participate in research, they should be involved in the process if they are able to "assent" by having a study explained to them and/or by reading a simple form about the study, and then giving their verbal choice about whether they want to participate. They may also provide a written assent if they are older. See WORKSHEET Children for circumstances in which a child's assent may be unnecessary or inappropriate.
 - a. Will assent be obtained for:

All research procedures and child groups	→ Go to question 7.2.
X None of the research procedures and child groups	→ Use the table below to provide justification, then skip to question 7.6
Some of your research procedures and child groups	→ Use the table below to identify the procedures for which assent will not be obtained.

Be sure to consider all research procedures and plans, including screening, future contact, and sharing/banking of data and specimens for future work.

Children Group ¹	Describe the procedures or data/specimen collection (if any) for which assent will NOT be obtained	Reason why assent will not be obtained
Children ages 12-36 months	All research procedures	Reason 46.108(a)/50.55- The capability of the children is limited by age that they cannot reliably be consulted for assent. Parent consent/permission will be documented

Table footnotes

- 1. If the answer is the same for all children groups or all procedures, collapse your answer across the groups and/or procedures.
- **7.2 Assent process.** Describe how assent will be obtained, for each child group. If the research involves children of different ages, answer separately for each group. If the children are non-English speakers, include a description of how their comprehension of the information will be evaluated.

7.3 Dissent or resistance. Describe how a child's objection or resistance to participation (including non-verbal indications) will be identified during the research, and what the response will be.

Although we will not be seeking assent due to child age, as pediatric rehabilitation professionals the research team is well-trained to recognize signs of dissent or resistance, such as negative facial expressions or crying. When this behavior occurs, the research team will temporarily discontinue research activities and/or cue caregivers to discontinue research activities and provide a break before resuming activities. It is anticipated that these behaviors may be more prevalent at the onset of research activities and new experiences, but will diminish over time. If this does not occur, caregivers will be provided with resources and suggestions to mitigate these behaviors using play-based, developmental strategies. If these behaviors persist after these strategies are implemented, caregivers will be reminded of their right to withdraw from the study at any time.

7.4 E-consent. Will any electronic processes (email, websites, electronic signatures, etc.) be used to present assent information to subjects/and or to obtain documentation (signatures) of assent? If yes, describe how this will be done.

7.5 Documentation of assent. Which of the following statements describes whether documentation of assent will be obtained?

None of the research procedures and child groups	→ Use the table below to provide justification, then go to question 7.5.b
All of the research procedures and child groups	→ Go to question 7.5.a , do not complete the table
Some of the research procedures and/or child groups	

Document Date & Version

	→ Complete the table below and then to go question 7.5.a
Children Group ¹	Describe the procedures or data/specimen collection (if any) for which assent will NOT be documented
Table footnates	

- Table footnotes
- 1. If the answer is the same for all children groups or all procedures, collapse the answer across the groups and/or procedures.
 - **a. Describe how assent will be documented**. If the children are functionally illiterate or are not fluent in English, include a description of the documentation process for them.
 - **b.** Upload all assent materials (talking points, videos, forms, etc.) to *Zipline*. Assent materials are not required to provide all of the standard elements of adult consent; the information should be appropriate to the age, population, and research procedures. The documents should be in Word, if possible.

7.6 Children who reach the legal age of consent during participation in longitudinal research.

Children who were enrolled at a young age and continue for many years: It is best practice to re-obtain assent (or to obtain it for the first time, if it was not obtained at the beginning of their participation). Children who reach the legal age of consent: Informed consent must be obtained from the now-adult subject for (1) any ongoing interactions or interventions with the subjects, or (2) the continued analysis of specimens or data for which the subject's identify is readily identifiable to the researcher, unless the IRB waives this requirement.

a. Describe the plans (if any) to re-obtain assent from children.

37/4		
N/A		
1 1/21		

- **b.** Describe the plans (if any) to obtain consent for children who reach the legal age of consent.
 - If adult consent will be obtained from them, describe what will happen regarding now-adult subjects who cannot be contacted.
 - If consent will not obtained or will not be possible: explain why.

N/A

- **7.7 Other regulatory requirements**. (This is for information only; no answer or response is required.) Researchers are responsible for determining whether their research conducted in schools, with student records, or over the Internet comply with permission, consent, and inspection requirements of the following federal regulations:
 - PPRA Protection of Pupil Rights Amendment
 - FERPA Family Education Rights and Privacy Act
 - COPPA Children's Online Privacy Protection Act

